3.5 Handling of Missing Data

For the classification of Treatment emergent adverse event (TEAE) and Concomitant medication, the following will be applied in the following order:

- a. If all dates/times (start and stop) missing, the event/medication will automatically be classified as a TEAE/Concomitant medication.
- b. For AEs with a missing start date/time, if the event end date/time is prior to first study drug administration, the event will not be classified as a TEAE.
- c. If only the AE start year/ medication end year is present and is the same or is after the first study drug administration year unit, the event/medication will be classified as a TEAE/Concomitant medication.
- d. If the AE start month and year/medication end month and year are present and are the same or after the first study drug administration month and year units, the event/medication will be classified as a TEAE/Concomitant medication.

For the efficacy analysis of values that are below the LLOQ, the following imputations will be made for continuous data analyses:

- HBsAg LLOQ/TND values will be set to $0.015[\log_{10}(0.015) = -1.852]$
- HBsAg LLOQ/TD values will be set to the midpoint between LLOQ/TND and LLOQ/TD.
- HBV DNA LLOQ/TND values will be set to 10 ($\log_{10}(10) = 1$).
- HBV DNA LLOQ/TD ($< 1.30 \log \text{ IU/mL}$) values will be set to the midpoint of LLOQ/TND (the midpoint = 1.15)
- HBV DNA = “insufficient sample” will be set to missing.
- HBcrAg LLOQ/TND values will be set to 30 ($\log_{10}(30) = 1.5$).

- HBcrAg LLOQ/TD (<3.0 log U/mL) values will be set to 2.25 (log U/mL)
- HBcrAg = “insufficient sample” will be set to missing.
- HBV-pgRNA = “insufficient sample” will be set to missing.
- HBV-pgRNA LLOQ/TND values will be set to 100 ($\log_{10}(100) = 2$).
- HBV-pgRNA values = “<4.04” will be set to 3.02 log C/mL
- HBV-pgRNA LLOQ/TD values will be set to the midpoint of LLOQ/TND (the midpoint = 3.02 log C/mL)

For the handling of missing primary efficacy data (excluding LLOQ/TND and LLOQ/TD), missing primary efficacy data (HBsAg) will be imputed using multiple imputation process (MI SAS procedure) with MAR pattern. For completeness, analysis will be repeated under the scenario of no imputation.

The Multiple imputation will be performed as follows:

- Missing data will be imputed using multiple imputation technique with Markov chain Monte Carlo method assuming MAR and multivariate normality.
- This is carried out by using the SAS procedure PROC MI with the MCMC option, the seed number will be 20201113. The number of burn-in iterations will be 200, which is the default value. Nevertheless, if diagnosis plots show that the convergence has not yet occurred, this will be adjusted.
- Imputation will be repeated N=1000 times. The $\log_{10}(\text{HBsAg})$ will then be calculated for each of the data set.

SAS Code:

```
Proc mi data=new nimpute = 1000 out= mi_mvn seed= 20201113;
  mcmc nbiter =200 plots=trace ;
  By Treatment;
  Var Baseline log10(HBsAg);

Run;
```

- The difference in HBsAg ($\Delta \log_{10}$) from Day 1 to Week 16 between treatment and placebo will be analysed using a general linear model for repeated measures for each imputation.

SAS Code:

```
Proc mixed data= mi_mvn ;
  By _imputation_;
  Class ID TRT VISIT HBeAg;
  Model CHG = Baseline HBeAg TRT VISIT TRT*VISIT /
  SOLUTION CL;
  DDFM=KenwardRoger;
  Repeated VISIT /SUBJECT = ID TYPE = UN ;
  Lsmeans TRT*VISIT / DIFF CL;

Run;
```

- The parameter estimates obtained from the above are then combined and reported using SAS - Proc mianalyze procedure.

Conversion of categorical values

In some instances, continuous variables are expressed as a range (i.e. < 10). In such cases, values may be converted to the range boundary (upper or lower limit as applicable). As an example, a value of <10 may be converted to 10. Such substitutions will be clearly documented in the footnotes of relevant outputs.

There will be no imputations or substitution made for missing safety data points.

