#### *11.3.3.1. Primary Efficacy*

The primary endpoint, HBsAg decline ( $\Delta \log_{10}$ ) from Day 1 to Week 16 of treatment will be analysed using a general linear model for repeated measures, using the stratification factors as independent variables in the model (A Genotype [yes, no] and HBeAg pos [yes, no]). The primary analysis will be based on the ITT set. The analysis will be repeated based on the mITT and PP sets, as sensitivity analyses.

The analysis will be based on a one-sided test at a 5% level of significance.

Note that the sample size calculations are based on a t-test, as power calculations based on a repeated measures model require information about within-patient correlation structures, which is not available. However, using a repeated measures model, better power is expected compared to a t-test. A t-test, imputing missing data at 16 weeks as zero difference versus baseline, will be carried out as a sensitivity analysis.

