3.3 Inferential Analyses

Descriptive statistics will be used to summarize the safety and PK data. No formal hypothesis testing is planned. All efficacy analyses (unless otherwise specified) will be performed at a one-sided 5% level of significance.

- HBsAg decline ($\Delta \log_{10}$) from Day 1 to Week 16 of treatment (primary)
 - Hypothesis:
 - H₀₁: Adjusted Mean for experimental arm at Week xx minus Adjusted Mean for control arm at Week xx = 0, where xx = 2, 4, 6, 8, 10, 12, 14, and 16
 - H₁₁: Adjusted Mean for experimental arm at Week xx minus Adjusted Mean for control arm at Week xx = -1, where xx = 2, 4, 6, 8, 10, 12, 14, and 16.

- Time Points: Change from baseline until to Week 16 of treatment.
 - A general linear model for repeated measures will be used to assess HBsAg decline ($\Delta \log_{10}$), using the stratification factors as independent variables in the model (HBeAg pos [yes, no]). Baseline HBsAg level will be included as a covariate. The analysis will be based on a one-sided test at a 5% level of significance. Degrees of freedom calculation will be based on the Kenward-Roger method. The unstructured covariance matrix structure to model the within-patient errors will be selected initially. If the unstructured covariance structure leads to non-convergence, covariance matrix structure will be selected through the maximum likelihood method. The final model will then we rerun by using the reduced maximum likelihood method.
- The following covariates will be included for this model:
- i. Baseline HBsAg level
 - ii. HBeAg positive [yes, no]
 - iii. Treatment Group
 - iv. Study visit
 - v. Interaction between treatment group and study visit
- The least-squares mean change from baseline, along with corresponding 95% CI and SE for treatment arms and experimental arm versus control arm at the one-sided 0.05 level will be provided for Week 2, 4, 6, 8, 10, 12, 14 and 16 for the ITT population (with Multiple imputation). This will be repeated for ITT (with no imputation), mITT (with Multiple imputation), mITT (with no imputation), PP set (with Multiple imputation) and PP set (no imputation).
 - If applicable, this model will be re-analyzed with the genotype covariate as “sensitivity analysis”.
- Liver Fibrosis and inflammation change from baseline from Day 1 to Week 16 of treatment
 - Hypothesis:

H_0 : Adjusted Mean for experimental arm at Week xx minus Adjusted Mean for control arm at Week xx = 0, where xx = 4, 8, 12 and 16

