15. CHANGES TO THE PLANNED ANALYSIS

Safety review will be performed when 20 patients have reached w8 (expected by 1st March 2021 with data cut-off point defined to be 5th March 2021, replacing when 50% (n=25) patients reach week 8.

Sponsor decided on February 17th, 2021 to suspend further enrollments (after approx. 25 randomizations).

A request to deviate from the protocol has been initiated and executed by the sponsor and will be documented here. The changes to the planned analysis from the protocol are described in the following table:

Protocol	Key Changes
Based on the protocol section 11.3.3.1, for the primary efficacy endpoints (HBsAg decline), imputing missing data at 16 weeks as zero difference versus baseline	
 ▪ Missing primary efficacy data (HBsAg) will be imputed using multiple imputation process (MI SAS procedure) with MAR pattern.
Not in the protocol	
 ▪ Inferential Analyses for liver Fibrosis and inflammation change from baseline from Day 1 to Week 16 of treatment ▪ To summarize the Maximum CTCAE for ALT, AST, BILI and GGT for Post Treatment Assessments using CTCAE to do the toxicity grading.
Not in the protocol - The primary efficacy variables	
 ▪ Additional primary efficacy variable: 
 ▪ Anti-HBs ▪ Anti-HBe.
Based on the protocol section 11.3.3.1, for the primary efficacy endpoints (HBsAg decline), A Genotype [yes, no] needs to be included in the general linear model	
 ▪ A Genotype variable will be removed from the general linear model because the CRAs went back and cross checked there is no available historical genotype available in the medical history source other than what is currently in the EDC and also for most of the patients, there is no virus available in the samples to genotype.

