18. TABLES

Table Number	Table Title	Population	DSMC Safety	DSMC Safety and Futility
14.1	Demographics and Other Baseline Characteristics			
14.1.1	Summary of Participant Enrolment and Disposition	ITT	X	X
14.1.2.1	Summary of Demographics and Baseline Characteristics	ITT		
14.1.2.2	Summary of Demographics and Baseline Characteristics	mITT		
14.1.2.3	Summary of Demographics and Baseline Characteristics	Safety	X	X
14.1.2.4	Summary of Demographics and Baseline Characteristics	PP		
14.1.3.1	Summary of Viral Serology at Screening	ITT		
14.1.3.2	Summary of Viral Serology at Screening	mITT		
14.1.3.3	Summary of Viral Serology at Screening	Safety		
14.1.3.4	Summary of Viral Serology at Screening	PP		
14.1.4	Summary of Treatment Compliance	Safety	X	X
14.2	Efficacy			
14.2.1.1.1	Summary of HBsAg by A Genotype – Imputation	ITT		X
14.2.1.1.2	Summary of HBsAg by A Genotype – No imputation	ITT		X
14.2.1.2.1	Summary of HBsAg by A Genotype – Imputation	mITT		
14.2.1.2.2	Summary of HBsAg by A Genotype – No Imputation	mITT		

14.2.1.3.1	Summary of HBsAg by A Genotype - Imputation	PP		
14.2.1.3.2	Summary of HBsAg by A Genotype – No Imputation	PP		
14.2.2.1.1	Analysis of HBsAg: Baseline to Week 16 – Imputation	ITT		X
14.2.2.1.2	Analysis of HBsAg: Baseline to Week 16 – No Imputation	ITT		X
14.2.2.2.1	Analysis of HBsAg: Baseline to Week 16 - Imputation	mITT		
14.2.2.2.2	Analysis of HBsAg: Baseline to Week 16 – No Imputation	mITT		
14.2.2.3.1	Analysis of HBsAg: Baseline to Week 16 – Imputation	PP		
14.2.2.3.2	Analysis of HBsAg: Baseline to Week 16 – No Imputation	PP		
14.2.3.1	Summary and Analysis of HBsAg Loss Rate A	ITT		X
14.2.3.2	Summary and Analysis of HBsAg Loss Rate B	ITT		X
14.2.4.1	Summary and Analysis of HBsAg Responder Rate A	ITT		X
14.2.4.2	Summary and Analysis of HBsAg Responder Rate B	ITT		X
14.2.5	Summary of HBsAg Relapse Rate	ITT		
14.2.6	Summary of Virologic Failure Rate of HBV DNA	ITT		X
14.2.7	Summary of HBV-pgRNA	ITT		X
14.2.8	Summary of HBcrAg	ITT		X
14.2.9	Summary of HBeAg	ITT (HBeAg+ patients)		X
14.2.10	Summary of Fibroscan VCTE	ITT		X
14.2.11	Summary of HBsAg Loss Rate (Target not detected vs. Target detected)	ITT		

14.2.12	Summary of Anti-HBs	ITT		
14.2.13	Summary of Anti-HBe	ITT		
14.2.14	Summary of PD Markers	PD		
14.3	Safety			
14.3.1	Summary of Concomitant Medication	Safety	X	X
14.3.3	Adverse Events			
14.3.3.1	Summary of Overall Treatment Emergent Adverse Events	Safety	X	X

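### SAP 15 drops the protocol's zero-change sensitivity t-test, so no planned primary analysis departs from MAR, and the multiple-imputation code in SAP 3.5 has no visit term

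*SAP*

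**What the plan says.** **Protocol.** Section 11.3.3.1 makes a repeated-measures model in the ITT set the primary analysis and adds: "A t-test, imputing missing data at 16 weeks as zero difference versus baseline, will be carried out as a sensitivity analysis". Section 11.4.1 also assumes zero change for drop-outs because the ITT population is analysed, and scales the effect from -1.0 to -0.9 for the sample size.

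**SAP, choice of analyses.** Section 3.3 lists the repeated-measures results first "for the ITT population (with Multiple imputation"). It then repeats them for ITT without imputation and for mITT and PP, each with and without imputation. Section 3.5 states that the imputation assumes MAR and adds: "For completeness, analysis will be repeated under the scenario of no imputation". Section 18 accordingly lists Table 14.2.2.1.2, "Analysis of HBsAg: Baseline to Week 16 – No Imputation", in the ITT set.

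**SAP, stated change.** The first row of the table in section 15 describes the protocol's position as "for the primary efficacy endpoints (HBsAg decline), imputing missing data at 16 weeks as zero difference versus baseline" and puts multiple imputation under MAR in its place. Section 2.4 still sizes the trial on zero change for drop-outs.

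**SAP, code.** In section 3.5, PROC MI runs by treatment with the variable list "Var Baseline log10(HBsAg"). The output goes directly into a PROC MIXED step that needs one row per patient and visit. The text above the code says log10(HBsAg) "will then be calculated for each of the data set", that is, after imputation, although the variable list already imputes it on that scale.

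**The concern.** There are two separate problems, and the first carries more weight.

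1. A sensitivity analysis that the protocol committed to has gone, and the SAP 15 row does not say that it was one. It is also the only planned analysis that asks whether the result survives if drop-outs have no HBsAg change, the assumption behind N=49. At stake is whether the report can say anything about departures from MAR.

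2. The first-listed primary analysis cannot be reproduced from the text. The input layout is not given, the imputation scale is stated two ways, and HBeAg is in the analysis model but not in the imputation model. Two competent programmers could produce different lead estimates, and one plausible program pulls imputed Week 16 values toward the arm's average over all visits.

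**Working it through.** **Inputs from the documents.** Week 16 effect -1.0, SD 1.08, one-sided alpha 0.05, power 80%, ratio 3:1 (37:12), 10% drop-out over the total study duration (Protocol 11.4.1; SAP 2.4). Week 12 effect -0.5, SD 0.7 (Protocol 11.5). Recruitment status, SAP 15: "Sponsor decided on February 17th, 2021 to suspend further enrollments (after approx. 25 randomizations").

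**Assumptions not in the documents.** A 19:6 split of those 25 patients, the effect path between the stated points, a baseline SD (0.8) and visit correlations (0.6 or 0.9) for the simulations, and drop-out spread evenly over visits.

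**The plan's own figure.** Control-arm n = (1 + 1/3) × (1.645 + 0.842)² × 1.08² / 0.9² = 11.87, or 47.5 in total. Exact t-test power for -0.9 is 80.1% at N=49 in exact 3:1 and 79.6% at 37:12. The planned 49 is reproduced, and it rests on zero change for drop-outs.

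**Which analyses remain.**

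| Analysis | What it assumes about missing Week 16 data |
|---|---|
| ITT, imputed | MAR, as stated |
| ITT, no imputation | MAR, through the repeated-measures likelihood |
| mITT and PP, with or without imputation | Restricted to patients with a Week 16 assessment (SAP 4.1.2, 4.1.6) |

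No t-test is listed in SAP 3.3, 3.5, 12.1 or 18, so none of the six applies zero change to drop-outs.

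**Size of the first problem.** If 10% drop out and return to baseline, the true effect is -1.0 × 0.9 = -0.90. Simulated at 37:12 (500 trials, visit correlation 0.9):

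- full data: -0.898
- visit-specific MAR imputation: -0.994
- SAP code in a one-row-per-visit layout: -0.940
- zero-change t-test: -0.902

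If drop-out is random instead, completer and zero-change t-tests on the same data with 10% missing have power of about 83% and 82% at 37:12, and about 56% and 55% at 19:6. At 19:6 they disagree on significance in about 4% to 6% of trials at 5% to 10% missing.

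**Size of the second problem.** In a one-row-per-visit layout, an imputed Week 16 value is centred on the arm's all-visit relation to baseline. With a share m missing at random, the estimated effect is -1 + m × (1 + mean effect over the eight visits). On a linear path to -0.5 at Week 12 and then to -1.0 at Week 16, the effects at Weeks 2 to 12 sum to -1.75. Adding -0.75 and -1.0 gives -3.5, and -3.5/8 = -0.4375. Hence:

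- m = 5%: -1 + 0.05 × 0.5625 = -0.97
- m = 10%: -1 + 0.10 × 0.5625 = -0.94
- m = 20%: -1 + 0.20 × 0.5625 = -0.89

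Other assumed early paths give -0.93 to -0.96 at 10%. Since the planned 10% runs to Week 40, about 5% may be nearer at Week 16.

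The standard error is 1.08 × √(1/37 + 1/12) = 0.36, or 0.51 at 19:6, so the 0.056 shift at 10% is 0.16 or 0.11 standard errors. A 37:12 simulation with 10% missing agrees: -0.933 against -0.989 with full data and -0.988 with visit-specific imputation.

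Under the null, the one-row-per-visit code rejected in 3.9% and 5.1% of trials at 37:12 (10% and 20% missing) and in 5.7% at 19:6 (10% missing, 1,500 trials). These are consistent with 5%.

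**The case against.** The strongest reply has four parts.

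- SAP 15 records the move to multiple imputation openly, in an exploratory phase 2a trial. Protocol 11.4.1 itself ties zero change to the ITT analysis, so the SAP's account of the protocol has some basis. This stands, but 11.3.3.1 is explicit that the t-test is a sensitivity analysis, and a row that reconciles neither passage still leaves it unlisted.
- The code is schematic: it puts a function in a variable list, places the degrees-of-freedom option outside the MODEL statement, and names the arm two ways. Multivariate normality suggests one column per visit, in which case the shift disappears. This stands as a limit on size. It does not settle the layout, because the next step needs one row per visit and no reshaping is shown.
- The unaffected no-imputation ITT table is already planned beside the imputed one. True, and that makes the fix cheap.
- Zero change is single imputation and only one of several departures from MAR. True, but it is the one the protocol planned and sized the trial on.

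Three stronger readings are tempting and not supported. A reader might compare power of 86% with 80% (37:12) or 61% with 53% (19:6) as the cost of dropping the t-test. Those figures set -1.0 with nothing missing against -0.9; on the same incomplete data the gap is about 1 to 2 points. A reader might infer a false-positive risk from the code, but the shift is toward zero. A reader might also infer that visit-specific imputation by arm must fail, since nine variables need 9 + 45 = 54 parameters and about 6 placebo patients give a covariance of rank 5. The split is not stated, SAP 3.7 still shows 12 placebo patients, the problem needs missing placebo data, and a prior or pooling would resolve it.

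**Conclusion.** Wrong as written, on both counts, with modest consequences.

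The loss of the zero-change t-test is a matter of document comparison and does not depend on any assumption: no planned primary analysis departs from MAR. Its effect depends on why patients leave. If 10% return to baseline, MAR imputation with visit-specific columns overstates the effect by about 0.09 log10 (0.994 - 0.902 = 0.092). If drop-out is random, the two t-tests rarely differ in conclusion.

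The imputation code is ambiguous on layout and scale whichever way it is read. The shift of 0.03 to 0.11 log10 toward zero at 5% to 20% missing holds only for a one-row-per-visit layout and an effect that grows over visits as Protocol 11.5 assumes. It concerns a reproducible lead estimate, not type I error. SAP 15 documents the change of method, so nothing here implies concealment.

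**What to change.** Before the Week 16 database lock and unblinding described in SAP 16.1:

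1. Restore the Week 16 zero-change t-test in SAP 3.3 as an ITT sensitivity analysis, with one table.
2. Correct the SAP 15 row to say that Protocol 11.3.3.1 planned zero change as a sensitivity analysis, and reconcile it with the sample-size text in 11.4.1.
3. Lead with the ITT repeated-measures model without imputation (Table 14.2.2.1.2).
4. If multiple imputation is kept as supportive, specify it in full: log10 scale, one row per patient, arms pooled with no BY statement, and Baseline, HBeAg, treatment and a column for each visit in the model. With all eight visits that is 11 variables and 11 + 66 = 77 parameters, so state how the model is kept estimable with about 25 patients, for example a ridge prior. All eight visits must stay, because SAP 3.3 and the shell for Table 14.2.2.x report each of them. Then show the reshape to one row per visit and the derivation of the change from baseline before PROC MIXED.

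The cost is one extra table, relabelling of planned outputs and one rewritten code block. The drawback of pooling is that it assumes a common covariance across arms.

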16. INTERIM AND FINAL ANALYSIS

16.1 Interim Analysis (DSMC Review meeting)

An unscheduled DSMC review meeting of all available unblinded preliminary safety study data will be conducted when any stopping rules (Protocol Section 4.6) are met in two or more patients. All stopping rules will be listed by treatment group.

Two DSMC Review meeting are scheduled:

1. DSMC Safety Review Meeting on all available unblinded preliminary safety study data:
Safety assessment when 40.8% (n=20 out of 49) patients reach week 8 resulting in a decision on continuation of the study based on safety (Go/No go decision); enrolment would remain ongoing during this review.
2. DSMC Safety Review and Futility Analysis Meeting on all available unblinded preliminary virology, safety, PK and PD study data:
Safety and futility when 50% patients (n=25) reached week 12, resulting in a decision on continuation of the study (Go/No go decision) based on safety and evidence of a benefit of EYP001 (HBsAg, other secondary viral markers); enrolment is ongoing during this review.

The DSMC review meeting will be performed on all available primary and secondary endpoints according to the DSMC charter, which describes the overall guidelines, composition, roles, and responsibilities of the independent DSMC for the EYP001-201 study, including the selection of DSMC members, timing of meetings, methods of providing information to and from the DSMC, frequency and format of meetings, data analysis recommendations, and DSMC relationships with other parties participating in the conduct of this study.

The futility assessment will be performed to determine if EYP001 has no benefit at a point when 50% of patients have reached 12 weeks of dosing. The futility assessment will be performed by the DSMC according to the following rules:

- A treatment effect of -1.0 on a log₁₀ scale of HBsAg for the primary endpoint at 16 weeks, and a common standard deviation of 1.08 was assumed and the treatment effect would be -0.5 after 12 weeks of treatment, with common standard deviation of 0.7 Using a one-sided alpha of 0.05 and 80% power (beta = 0.20), a group sequential design, incorporating a futility and efficacy O'Brien-Fleming analysis when 50% of patients have reached 12 weeks of treatment, needs inclusion of 49 patients.
- Table 2 gives the probability of stopping early under the null and alternative hypothesis, at the time of the interim analysis.

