LS mean is derived from a general linear model for repeated measures. The covariates are treatment groups, visit, baseline HBsAg, A Genotype, HBeAg positive and the interaction term of treatment group*visit.

Covariance structure is XXX.

CI = Confidence Interval. SE = Standard Error.

Programming Note:

- Repeat for table 14.2.2.1.2 (ITT set with no imputation), 14.2.2.2.1 (mITT with imputation), 14.2.2.2.2 (mITT with no imputation), 14.2.2.3.1 (PP set with imputation) and 14.2.2.3.2 (PP set with no imputation) .

-The SAS code used to implement this analysis is given below:

```
PROC MIXED DATA=dataset;
  CLASS ID TRT VISIT HBeAg;
  MODEL CHG = Baseline HBeAg TRT VISIT TRT*VISIT / SOLUTION CL;
  DDFM=KenwardRoger;
  REPEATED VISIT /SUBJECT = ID TYPE = UN ;
  LSMEANS TRT*VISIT / DIFF CL;
  RUN;
```

Table 14.2.3.1 Summary and Analysis of HBsAg Loss Rate A (ITT Set)

Visit	Category	Statistics	EYP001a 200 mg QD + NA daily (N=XXX)	Placebo + NA daily (N=XXX)
Week 16		n	xx	xx
	HBsAg Loss	n (%) [1]	xx (xx.x %)	xx (xx.x %)
		p-value	0.XXX	

<Repeat for Week 40>

Source Listing: 16.2.6.1

p-value is based on the Person Chi-squared Test.

HBsAg Loss is defined as HBsAg value < LLOQ/TND.

[1] Number of subjects at each visit (Visit n) will be used as the denominator for the calculation of all percentages.

Programming Note:

- Only present Week 16 and Week 40 will consider multiplicity by a combination of a hierarchical fixed test procedure and a Hochberg procedure to adjust p-value.

Table 14.2.3.2 Summary and Analysis of HBsAg Loss Rate B (ITT Set)

Visit	Category	Statistics	EYP001a 200 mg QD + NA daily (N=XXX)	Placebo + NA daily (N=XXX)
Week 16		n	xx	xx
	HBsAg Loss	n (%) [1]	xx (xx.x %)	xx (xx.x %)
		p-value	0.XXX	

<Repeat for Week 40>

Source Listing: 16.2.6.1

p-value is based on the Person Chi-squared Test.

HBsAg Loss is defined as HBsAg value < LLOQ/TD.

[1] Number of subjects at each visit (Visit n) will be used as the denominator for the calculation of all percentages.

Programming Note:

- Only present Week 16 and Week 40 will consider multiplicity by a combination of a hierarchical fixed test procedure and a Hochberg procedure to adjust p-value.

Table 14.2.4.1 Summary and Analysis of HBsAg Responder Rate A (ITT Set)

Visit	Category	Statistics	Decrease from Baseline \geq 1.0 on the log10 Scale	
			EYP001a 200 mg QD + NA daily (N=XXX)	Placebo + NA daily (N=XXX)
Week 16	HBsAg Responder	n		
		n (%) [1]		
		p-value		
Week 40		n	xx	xx

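### Primary model: one baseline HBsAg slope shared by all eight visits leaves the Week 16 contrast with little benefit from the baseline covariate

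*SAP*

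**What the plan says.** SAP 3.3 adds a covariate that the protocol's model (protocol 11.3.3.1) does not have: "Baseline HBsAg level will be included as a covariate". Its covariate list contains a single interaction, "Interaction between treatment group and study visit".

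The code in SAP 3.5 agrees: "Model CHG = Baseline HBeAg TRT VISIT TRT*VISIT", with "Repeated VISIT /SUBJECT = ID TYPE = UN". The programming note under mock Table 14.2.2.x repeats it for the other analysis sets and the unimputed data: "MODEL CHG = Baseline HBeAg TRT VISIT TRT*VISIT / SOLUTION CL".

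SAP 16.1 assumes an SD of 1.08 for the Week 16 endpoint and, for the interim look, "the treatment effect would be -0.5 after 12 weeks of treatment, with common standard deviation of 0.7". Protocol Table 1 shows SDs of HBsAg change of 0.1 at Day 29 in nearly every arm of the phase 1b study (0.2 in one).

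No model with a visit-specific baseline slope is planned, and no Week 16 ANCOVA. The only covariate re-analysis named in SAP 3.3 adds genotype.

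**The concern.** A main effect for baseline in a repeated-measures model forces the relation between baseline and change to be the same at Week 2 as at Week 16. If HBsAg hardly moves early and spreads out later, a patient's starting level can say little about the early change and possibly much about the late one. An unstructured fit gives most weight to the visits with the smallest variance, so it estimates the early, near-flat relation and applies it at Week 16.

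The covariate would then do least at the primary visit. What is at stake is precision in a small trial. SAP 15 records that enrolment was suspended after about 25 randomisations, and under SAP 3.4 the Week 16 primary test gates the Week 16 key secondary endpoints.

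**Working it through.** **1. The plan's own figure.** Inputs (SAP 2.4 and 2.5): effect 1.0 × 0.9 = 0.9, SD 1.08, allocation 37:12, one-sided 5%.

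- SE = 1.08 × √(1/37 + 1/12) = 1.08 × 0.3322 = 0.359.
- Power (normal) = Φ(0.9/0.359 − 1.645) = Φ(0.86) = 80.6%. The noncentral t gives 79.6%, and the sample size of 49 is reproduced.

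This calculation uses no baseline adjustment.

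**2. Where the shared slope comes from.** With complete data and unstructured covariance S, the shared slope is a weighted mean of the visit-specific slopes, with weights w = S⁻¹1 / (1ᵀS⁻¹1). For two visits with SDs s₁ < s₂ and correlation r, the later visit's weight is

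w₂ = (s₁² − r·s₁·s₂) / (s₁² + s₂² − 2r·s₁·s₂).

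Take only the SAP's Week 12 and Week 16 SDs (0.7 and 1.08), with r assumed to be 0.7:

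w₂ = (0.490 − 0.529) / (0.490 + 1.166 − 1.058) = −0.039/0.598 = −0.07.

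The weight is zero at r = 0.7/1.08 = 0.65 and negative above that. So the planning values alone can remove Week 16 from the slope estimate.

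For all eight visits, the SDs were interpolated through 0.1 (Week 4), 0.7 (Week 12) and 1.08 (Week 16). Under compound symmetry, AR(1) or independent increments, Week 2 carries 89% to 138% of the weight, and Week 16 about zero or slightly less. If the true slope grows with the SD or with time, the fitted slope is 0.4% to 12% of the true Week 16 slope.

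**3. What that does to Week 16 precision.** If the fitted slope is a fraction k of the true Week 16 slope, the share of the available variance reduction obtained is 1 − (1 − k)² = 2k − k². At k = 0.004 this is about 1%; at k = 0.12 it is 0.24 − 0.014 = 23%.

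**4. Could the slope be equal at all visits?** The Week 4 slope cannot exceed SD(Week 4)/SD(baseline), and the Week 16 slope is ρ × 1.08/SD(baseline). The ratio is therefore at most 0.1/(1.08ρ): 31% at ρ = 0.3 and 19% at ρ = 0.5. With these SDs a constant slope is not feasible.

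**5. What a Week 16 slope would give.** Here ρ is the size of the correlation of baseline log10 HBsAg with Week 16 change. The plan does not give it. SE = 0.359 × √(1 − ρ²).

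| ρ | SE with own slope | Power, own slope (noncentral t) | Power, SAP model (analytic) |
|---|---|---|---|
| 0.3 | 0.342 | 82.8% | 79.6–80.3% |
| 0.5 | 0.311 | 88.7% | 79.7–81.7% |

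Simulation at 37:12, with HBeAg as a main effect in both models (3,000 trials):

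| ρ | SAP model | With Baseline*VISIT |
|---|---|---|
| 0.5 | 80.8% (SE 0.354) | 88.9% (SE 0.311) |
| 0.3 | 80.8% | 82.6% |
| 0 | 80.4% | 79.1% |

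At ρ = 0.5 the shared slope averaged −0.02 against a true Week 16 slope of −0.68. Type I error was 5.2% and 5.5%. A repeat simulation gave gains of about 3 points at 0.3 and 6 at 0.5, and a loss of 0.5 to 1 at 0.

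At 19:6 and ρ = 0.5, runs of 500 and 600 trials gave 50% to 60% and 52% to 61%. Monte Carlo error is about 2 points on each figure, so these are consistent with a gain of the same order as at 37:12.

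**6. Boundary cases.** With SD flat at 1.08 and ρ = 0.5, both models give 87.7%. With a milder rise (SD 0.35 at Week 4) the gain at ρ = 0.5 is 6 points (82.9% to 89.0%). If the SD is already 0.35 at Week 2, the share of variance reduction obtained by the SAP model ranges from about −40% to 59%, depending on the correlation structure.

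**The case against.** **The size rests on numbers the plan does not contain.** The correlation of baseline with change is assumed. The SD profile joins an observed one-decimal value from small phase 1b arms, 90% HBeAg negative and treatment naive (protocol 1.4.3), to two planning assumptions, and the SDs at most other visits are interpolated. This stands. The near-zero slope depends on the 0.1. The planned rise from 0.7 to 1.08 still implies growth in variance, and the milder profile still shows a gain.

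**A reader might infer that the SAP's expectation of better power fails.** The documents do not support that. The statement in SAP 2.4 is carried over from protocol 11.3.3.1 and 11.4.1, where the model has stratification factors and no baseline covariate. It credits the repeated measures, not baseline adjustment. N=49 comes from an unadjusted t-test.

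**A reader might also infer that HBeAg needs the same treatment.** HBeAg is restricted in the same way, but nothing shows a benefit from freeing it. In simulation HBeAg*VISIT only cost power: about 1 more point at 37:12. With both terms at 19:6 and no baseline correlation, the total loss was about 2 points in one simulation and 4 in another (53.2% to 49.4%).

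**The unstructured fit may not survive.** Eight visits need 8 × 9/2 = 36 covariance parameters from about 25 patients. On non-convergence SAP 3.3 selects another structure, and one with homogeneous variance would not weight early visits this way. The simulations used complete data and n − 4 degrees of freedom, not multiple imputation with Kenward-Roger. This stands, and it is why the fix needs a fallback.

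**Conclusion.** The structural point is certain: the text and both blocks of code fit one baseline slope for all visits. With an unstructured covariance and SDs that rise as the documents suggest, the Week 16 contrast gets little or no benefit from the covariate the SAP added.

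The consequence is lost precision only. It would be wrong to read this as bias or an inflated type I error: randomisation keeps the Week 16 contrast unbiased, and the simulated error rates are close to 5% under both models. Planned power near 80% at N=49 is not contradicted.

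The gain forgone is about 2 to 3 power points at a correlation of 0.3 and 6 to 8 at 0.5 with 37:12, and similar at 19:6. There is none if the variance is flat over time. The point is a cheap improvement, not a defect that invalidates the analysis. Confidence in the size is moderate because the correlation and most visit SDs are assumed.

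**What to change.** In SAP 3.3, the SAP 3.5 code and the Table 14.2.2.x code, use `MODEL CHG = Baseline Baseline*VISIT HBeAg TRT VISIT TRT*VISIT`, and state that Baseline is on the log10 scale. Do not add HBeAg*VISIT.

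Prespecify that, if this model does not converge at about 25 patients, the fallback is a Week 16 ANCOVA on baseline log10 HBsAg and HBeAg. In simulation at correlation 0.5 the ANCOVA had 87.4% power at 37:12 and 57.6% at 19:6, against 80.6% and 50% for the model as written.

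The cost is one line of text and code and 7 more fixed-effect parameters. If baseline is unrelated to change, power falls by about 1 point at 37:12 and 1 to 2 at 19:6. If variance is flat over time, there is no gain, and a loss of 1 to 3 points at the smaller size.
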